1.5 Rationale

There has been a limited benefit from anti-angiogenesis drugs in patients with NSCLC. Bevacizumab provides a modest survival improvement when added to chemotherapy and VEGFR tyrosine kinase inhibitors have been associated with minimal efficacy as single agents and increased toxicity when combined with chemotherapy. We postulate that the response rates and survival may be improved with a better selection of patients based on abnormalities of the targets for the drugs. Since, despite the molecular selection prior to treatment, only a small percentage of patients will benefit from the treatment, we plan to further investigate those patients with whole exome sequencing in both the pre-treatment samples to identify the predictors for response and at the time of progression, with

repeated biopsy, in an attempt to identify the predictors for secondary resistance. By identifying more reliable predictors for response to pazopanib, our study may help to establish its role in the treatment of NSCLC.

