1.6 Correlative Studies

Patients enrolled in this study will undergo optional next generation sequencing of tumor samples taken prior to treatment and at the time of disease progression. Archived formalin fixed paraffin embedded (FFPE) samples must have adequate viable cells for next generation sequencing to be performed. This routine sequencing involves targeted exon sequencing of “clinically significant” cancer genes, and allows for targeted “deep” sequencing to detect single nucleotide variants, copy number variants, and structural variations which are frequently associated with mutated solid and hematological genomes. The assay interrogates the exon sequences of a number of genes that have been selected based on current sequencing test order patterns by oncologists or literature-based knowledge of known clinical relevance to specific tumor types.

The genomic landscape of cancer is complex and evolves through the process of clonal evolution innately and in response to treatment. Unbiased whole exome and transcriptome sequencing performed on tumor samples at time of diagnosis in responders and non-responders will help us identify unique variations that confer susceptibility to pazopanib. Moreover, genomic analysis at time of progression after treatment with pazopanib (after response lasting for 6 months or longer) will provide some unique insights into mechanisms underlying acquired resistance.

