2.2 Secondary Objectives

1. To correlate outcomes with specific mutations.
2. To further evaluate extreme responders with whole genome and transcriptome sequencing.
3. To evaluate the mechanisms of secondary resistance.

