9.0 CORRELATIVE STUDIES

9.1 Tumor Tissue For Research Purposes

With patient consent, archived formalin fixed paraffin embedded specimens from the time of diagnosis may be sequenced as part of the patient's routine care. If archival tissue samples are available and/or biopsy is obtained for clinical purposes at the time of disease progression, WUSM may request a tumor sample, with patient consent, for research purposes, including whole exome and transcriptome sequencing. The specimens will be collected in accordance with standard of care practice and will be taken to the Washington University Tissue Procurement Core for processing and storage per institutional practice.

For the purpose of eligibility, patients expressing pazopanib targeted genes in either tissue assays or peripheral blood should be considered for study.

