12.0 MEASUREMENT OF EFFECT

12.1 Antitumor Effect – Solid Tumors

For the purposes of this study, patients should be re-evaluated for response 8 weeks after initiation of pazopanib and then every 8 weeks thereafter. In addition to a baseline scan, confirmatory scans should also be obtained not less than 4 weeks following initial documentation of objective response.

Response and progression will be evaluated in this study using the new international criteria proposed by the revised Response Evaluation Criteria in Solid Tumors (RECIST) guideline (version 1.1) [Eur J Ca 45:228-247, 2009]. Changes in the largest diameter (unidimensional measurement) of the tumor lesions and the shortest diameter in the case of malignant lymph nodes are used in the RECIST criteria.

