12.4.3 Evaluation of Best Overall Response

The best overall response is the best response recorded from the start of the treatment until disease progression/recurrence (taking as reference for progressive disease the smallest measurements recorded since the treatment started). The patient's best response assignment will depend on the achievement of both measurement and confirmation criteria.

For Patients with Measurable Disease (i.e., Target Disease)

Target Lesions	Non-Target Lesions	New Lesions	Overall Response	Best Overall Response when Confirmation is Required*
CR	CR	No	CR	>4 wks. Confirmation**
CR	Non-CR/Non-PD	No	PR	>4 wks. Confirmation**
CR	Not evaluated	No	PR	
PR	Non-CR/Non-PD/not evaluated	No	PR	
SD	Non-CR/Non-PD/not evaluated	No	SD	Documented at least once >4 wks. from baseline**
PD	Any	Yes or No	PD	no prior SD, PR or CR
Any	PD***	Yes or No	PD	
Any	Any	Yes	PD	

* See RECIST 1.1 manuscript for further details on what is evidence of a new lesion.
 ** Only for non-randomized trials with response as primary endpoint.
 *** In exceptional circumstances, unequivocal progression in non-target lesions may be accepted as disease progression.
 Note: Patients with a global deterioration of health status requiring discontinuation of treatment without objective evidence of disease progression at that time should be reported as “symptomatic deterioration.” Every effort should be made to document the objective progression even after discontinuation of treatment.

For Patients with Non-Measurable Disease (i.e., Non-Target Disease)

Non-Target Lesions	New Lesions	Overall Response
CR	No	CR
Non-CR/non-PD	No	Non-CR/non-PD*
Not all evaluated	No	not evaluated
Unequivocal PD	Yes or No	PD
Any	Yes	PD

* ‘Non-CR/non-PD’ is preferred over ‘stable disease’ for non-target disease since SD is increasingly used as an endpoint for assessment of efficacy in some trials so to assign this category when no lesions can be measured is not advised

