14.0 STATISTICAL CONSIDERATIONS

14.1 Study Objectives and Endpoints

The primary objective of this study is to investigate the response rate and progression-free survival of single agent pazopanib in a molecularly selected population of patients with advanced NSCLC. Patients with advanced NSCLC and abnormalities in VEGFR or PDGFR will receive single agent pazopanib at 800 mg daily. Patients may elect at study entry to provide tissue, from either archival or freshly obtained tissue, for research purposes. Optional tumor tissue testing will include whole exome and transcriptome sequencing performed in 10 patients. This will include 4 to 6 responders and 4 to 6 non-responders in order to identify the predictors for benefit; initial predictors are the mutations in VEGFR or PDGFR, but sequencing will be used to evaluate for other predictors as well. Patients may also elect to submit tissue from any standard of care biopsy performed at the time of progression in an attempt to identify the mechanisms for secondary resistance.

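### Does the mismatch between 2.2 and 14.1 over which patients are sequenced, and by which assay, need a change to the plan?

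*Combined protocol and SAP*

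**What the plan says.** Secondary objective 2 in section 2.2 reads: "To further evaluate extreme responders with whole genome and transcriptome sequencing". The other sections describe the work differently.

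- Section 14.1 plans "whole exome and transcriptome sequencing performed in 10 patients" and adds: "This will include 4 to 6 responders and 4 to 6 non-responders in order to identify the predictors for benefit". Providing tissue is the patient's choice.
- Section 1.5 expects that "only a small percentage of patients will benefit from the treatment, we plan to further investigate those patients with whole exome sequencing", before treatment and at progression.
- Section 1.6 refers to "whole exome and transcriptome sequencing performed on tumor samples at time of diagnosis in responders and non-responders". For samples taken at progression it adds a condition, a response of at least 6 months.
- Section 9.1 says that "WUSM may request a tumor sample, with patient consent, for research purposes, including whole exome and transcriptome sequencing", where tissue is available.

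On response itself, 2.1 sets RECIST 1.1 for the primary objective and 12.4 defines the categories. Section 12.1 says that "confirmatory scans should also be obtained not less than 4 weeks following initial documentation of objective response". The footnote to the best-response table in 12.4.3 limits the confirmation rule: "Only for non-randomized trials with response as primary endpoint". This trial has one arm and response is a primary endpoint, so the rule applies.

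Section 14.2 calls the study a pilot of 20 patients, sized by feasibility, with a descriptive analysis.

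**The concern.** Three things look wrong on a first reading.

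1. **Assay and population.** Whole genome and whole exome sequencing are different assays, and extreme responders alone are a different group from responders plus non-responders. Taken literally, 2.2 and 14.1 cannot both describe the same work.
2. **Definitions and selection.** Extreme has no definition, and 14.1 does not tie responder to the RECIST categories. It does not class stable disease, or patients with non-measurable disease only. Nothing says which non-responders are taken, so comparators would be picked after response is known.
3. **The range itself.** Section 14.1 states 4 to 6 responders as if it were assured. Four is only the expected number at a 20% response rate, and 1.5 expects few patients to benefit.

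At stake are secondary objective 2 and the exploratory search for predictors. If comparators were picked selectively, or only a few responders had tissue, that comparison could mislead.

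**Working it through.** **1. The assay, section by section**

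| Section | Assay | Patients |
|---|---|---|
| 1.5 | whole exome | those who benefit |
| 1.6 | whole exome and transcriptome | responders and non-responders |
| 2.2 | whole genome and transcriptome | extreme responders |
| 9.1 | whole exome and transcriptome | consenting, tissue available |
| 14.1 | whole exome and transcriptome | 10 patients, 4 to 6 of each kind |

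Four sections agree on exome and one line differs. The populations can also be read together, with extreme responders as a subset of the responders and the non-responders as comparators. No section says so outright.

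**2. What responder means**

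Section 2.1 sets response by RECIST 1.1, and 12.4 defines complete response, partial response and confirmed best overall response. Section 14.2 uses responder for the patients counted in the response rate. Confirmed complete or partial response is therefore the natural reading. What is missing is an explicit link, and a line on stable and non-measurable disease.

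**3. The plan's own figures**

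Inputs from 14.2 are n = 20 and the rates 20% and 5%. With X ~ Binomial(20, p):

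- P(X ≥ 3) at p = 0.20 is 0.794 (plan: 80%).
- P(X ≥ 3) at p = 0.05 is 0.075 (plan: below 10%).
- The exact 80% interval for 4/20 is 9.0% to 36.1% (plan: 9% to 36%).

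All three reproduce, so the same model can be used for the range of 4 to 6.

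**4. How often the range is met**

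Assume that responder means complete or partial response. The documents give no tissue rate, so let f be the share of patients with usable tissue, independent of response. Responders with tissue then follow Binomial(20, p × f). For p = 0.20 and f = 1:

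P(X ≥ 4) = 1 − (0.0115 + 0.0576 + 0.1369 + 0.2054) = 1 − 0.4114 = 0.589.

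| True rate p | f | P(at least 4) | P(more than 6) | P(0 or 1) |
|---|---|---|---|---|
| 15% | 1 | 0.352 | 0.022 | 0.176 |
| 20% | 1 | 0.589 | 0.087 | 0.069 |
| 25% | 1 | 0.775 | 0.214 | 0.024 |
| 30% | 1 | 0.893 | 0.392 | 0.008 |
| 20% | 0.75 | 0.352 | 0.022 | 0.176 |
| 25% | 0.75 | 0.532 | 0.065 | 0.088 |
| 30% | 0.75 | 0.690 | 0.143 | 0.042 |
| 20% | 0.50 | 0.133 | 0.002 | 0.392 |
| 30% | 0.50 | 0.352 | 0.022 | 0.176 |

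A shortfall is common. An excess is uncommon once tissue is allowed for: at 20%, 25% and 30% it falls from 9%, 21% and 39% to 2%, 6.5% and 14% at f = 0.75.

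**5. What a shortfall costs**

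For one pre-chosen binary marker that separates the groups perfectly, the smallest one-sided permutation p-value among 10 patients is 1/C(10,4) = 1/210 at 4 versus 6 and 1/C(10,3) = 1/120 at 3 versus 7. Losing one responder barely moves this. Neither value would survive correction across the many genes that exome and transcriptome data cover, so the search is hypothesis-generating at either split.

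**The case for a change.** The best case for a change is that a selection rule is worth most before responses are known, and that a few lines would supply it. Section 13.0 also asks the semi-annual report to count patients who have met each objective, which is awkward for objective 2 while its population is unsettled. One could write that responder means confirmed complete or partial response, call 4 to 6 a target, and draw the comparators at random with a fixed seed.

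Part of this stands. The texts of 2.2 and 14.1 disagree, extreme is undefined, and no rule picks the 10 patients. It also cannot be said that the permutation analysis in 14.2 is untouched. Its worked example uses VEGFR1 expression, and transcriptome sequencing is the only research assay described that would measure expression, so that analysis may run on this set.

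The proposed remedy is weaker. A random draw gives up the choice of clear progressors as comparators, which is a reasonable design for finding predictors with 10 samples. With 3 responders, filling up to 10 needs 7 non-responders, above the plan's own limit of 6. Counting every other treated patient as a non-responder would include any who were never scanned. Since tissue is optional, the real choice may also be small: if only 10 patients give tissue, there is nothing to draw.

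**Conclusion.** No change to the plan is called for. The assay conflict is one line against four sections, and aligning it alters no result. The link from responder to the RECIST categories, the classing of stable disease and the handling of a shortfall are details that analysts can settle sensibly and state in the report, with the number sequenced in each group and how those patients were chosen. Random or purposive choice of comparators is a fair trade-off either way.

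The range of 4 to 6 is best read as an aim. At a 20% true rate it has a 59% chance of reaching its lower end with tissue from everyone, and 35% if three quarters give tissue. These figures assume that responder means complete or partial response and that giving tissue is independent of response; the tissue share is an assumption, since the documents give none.

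The reach is limited to an optional, exploratory comparison in at most 10 patients and possibly the expression example in 14.2, both descriptive. The response rate and progression-free survival estimates do not use the sequencing set. If the protocol is amended for another reason, 2.2 could be brought into line with 14.1 at the same time.

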14.2 Study Design and Analyses

This is an open label, single-arm pilot study to obtain preliminary information of the efficacy of single agent pazopanib. A total of N=20 patients will be enrolled for this study. The sample size is determined primarily based on clinical feasibility rather than statistical power. According to the general guidelines regarding sample size for pilot and translational study¹⁸, however, the proposed sample size will provide us a reasonable precision to estimate the preliminary information. If 4 responders are observed out of 20

patients, for example, we would have 80% confidence that the “true” rate would fall between 9% and 36%. If the “true” response rate is 20% or higher, there would be 80% chance of observing at least 3 responders out of 20 patients. Conversely, there would be <10% chance to observe 3 or more responders if the true rate is less than 5%.

As a pilot study for proof of principal, the data analysis will be descriptive in nature. Demographic and clinical characteristics of the sample, as well as response, toxicity by grade and loss to follow up will be summarized using descriptive statistics. Kaplan-Meier product limit estimator will be used to describe the distribution of progression free survival. The 95% confidence interval (CI) for RR and 6-month PFS will also be calculated. The association between response and specific mutation status will be assessed by permutation analysis. Taking the relationship between VEGFR1 expression and RR as an example, for instance, we first compute the observed test statistics, e.g., the sample mean difference between responders versus non-responders. Then to simulate the null distribution of the test statistics, or the distribution of the observed mean differences if there were truly no difference, we repeat the following 10,000 times: we randomly shuffle the response status, and then calculate the sample difference between the newly designated groups. The permutation p-value equals the proportion of simulations from the null distribution that exceed the observed test statistics.

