3.0 PATIENT SELECTION

3.1 Inclusion Criteria

1. Histologically confirmed diagnosis of advanced (metastatic or unresectable) non-small cell lung cancer (NSCLC) with mutations, rearrangement and fusion involving RET oncogene, or abnormalities in the pazopanib target genes defined as VEGFR1-3, PDGFRA, PDGFRB, or TP53 with abnormalities including deletion, insertion, early stop codon, and/or nonsynonymous mutations with functional consequences. CLIA certified lab testing for pazopanib target genes using cell free DNA from peripheral blood and/or assays performed on tumor tissues are acceptable.
2. Evaluable disease by imaging or physical exam OR measurable disease defined as at least one lesion that can be accurately measured in at least one dimension (longest diameter to be recorded) as ≥ 10 mm with CT scan, as ≥ 20 mm by chest x-ray, or ≥ 10 mm with calipers by clinical exam.
3. Failed at least one standard chemotherapeutic treatment for NSCLC.
4. At least 18 years of age.
5. ECOG performance status ≤ 2 (see Appendix A)
6. Normal bone marrow and organ function as defined below:
 - a. Absolute neutrophil count $\geq 1,500/\text{mcl}$
 - b. Platelets $\geq 100,000/\text{mcl}$
 - c. Hemoglobin ≥ 9.0 g/dL

- d. PT or INR $\leq 1.2 \times$ IULN
 - e. aPTT $\leq 1.2 \times$ IULN
 - f. Total bilirubin $\leq 1.5 \times$ IULN
 - g. AST(SGOT)/ALT(SGPT) $\leq 2.5 \times$ IULN
 - h. Creatinine ≤ 1.5 mg/dL OR creatinine clearance ≥ 30 mL/min/1.73 m² for patients with creatinine levels above 1.5 mg/dL
 - i. UPC < 1 or, if UPC ≥ 1 , 24-hour urine protein < 1 g; use of urine dipstick for renal function assessment is not acceptable.
7. Patients receiving anticoagulation therapy are eligible if their INR is stable and within the recommended range for the desired level of anticoagulation.
 8. Ability to swallow and retain oral tablets.
 9. Women of childbearing potential and men must agree to use adequate contraception (hormonal or barrier method of birth control, abstinence) prior to study entry and for the duration of study participation. Should a woman become pregnant or suspect she is pregnant while participating in this study, she must inform her treating physician immediately.
 10. Ability to understand and willingness to sign an IRB approved written informed consent document.

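### The permutation p-value, as worded, leaves out ties, so p-values for yes/no mutation status in 20 patients are far too small and can be exactly zero

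*Combined protocol and SAP*

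**What the plan says.** Section 2.2 (Secondary Objectives) lists as its first item: "To correlate outcomes with specific mutations". Section 14.2 gives the method: "The association between response and specific mutation status will be assessed by permutation analysis". It illustrates this with VEGFR1 expression. The statistic, offered as an example, is the difference in sample means between responders and non-responders. Response status is shuffled 10,000 times, and then: "The permutation p-value equals the proportion of simulations from the null distribution that exceed the observed test statistics".

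No section gives a rule for ties, adds one to numerator and denominator, or says whether the test is one- or two-sided. No significance threshold is set, and section 14.2 describes the work this way: "As a pilot study for proof of principal, the data analysis will be descriptive in nature".

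On what will be tested, section 14.1 says: "initial predictors are the mutations in VEGFR or PDGFR, but sequencing will be used to evaluate for other predictors as well". Section 3.1 admits patients with RET alterations or with "abnormalities in the pazopanib target genes defined as VEGFR1-3, PDGFRA, PDGFRB, or TP53". The sample size is fixed: "A total of N=20 patients will be enrolled for this study".

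**The concern.** A p-value is the null probability of a result at least as extreme as the one observed, so it must include the observed result. The word *exceed* leaves it out. For a continuous measurement, ties are rare and nothing is lost. Mutation status, however, is naturally yes or no for each gene. With 20 patients entering through several genes, some genes may have only one or two carriers. The shuffled statistic then has a handful of possible values, and the observed one can carry much of the null probability.

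At stake is the only method the plan gives for linking response to mutations. An analyst who codes the sentence as written would report p-values that are too small, and a value of exactly zero whenever the observed table is the most extreme possible in the tested direction. Chance patterns could then pass as predictors of response.

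A lesser point is direction. If the signed difference is used, a mutation associated with non-response gets a p-value near 1, although the objective states no direction.

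**Working it through.** **Inputs from the documents.** N = 20; 10,000 shuffles; statistic T = mean in responders minus mean in non-responders; p = proportion of shuffles strictly above the observed T. Section 14.2's own illustration begins "If 4 responders are observed out of 20", so 4 responders is the main case here.

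**Assumptions not in the documents.** The number of carriers per gene, the 3-responder case, and, for error rates only, a 0.05 threshold and the carrier prevalences.

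**The plan's stated figures.** The documents give no permutation p-value. The sample-size figures in section 14.2 do reproduce. The exact 80% interval for 4/20 is 9.0% to 36.1% (stated 9% to 36%). P(≥3 responders) is 0.794 at a true rate of 20% (stated 80%) and 0.075 at 5% (stated below 10%).

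**Method.** For yes/no status with r responders and k carriers, shuffling makes the number X of carriers among responders hypergeometric:

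P(X = x) = C(k, x) · C(20 − k, r − x) / C(20, r).

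T increases with X. The rule as written is therefore P(X > x observed). The valid one-sided value is P(X ≥ x observed), the one-sided Fisher p-value.

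**Worked case: r = 4, k = 10, x = 3.** C(20,4) = 4,845.
- P(X = 4) = 210/4,845 = 0.043.
- P(X = 3) = 120 × 10/4,845 = 0.248.
- As written: 0.043. With ties: 0.043 + 0.248 = 0.291. Two-sided with ties: 2 × 0.291 = 0.582, because these margins are symmetric.

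**Other cases.**

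| Responders | Carriers | Carriers responding | As written | Ties counted (one-sided) |
|---|---|---|---|---|
| 3 | 5 | 2 | 10/1,140 = 0.009 | (10 + 150)/1,140 = 0.14 |
| 4 | 2 | 1 | 6/190 = 0.032 | 70/190 = 0.37 |
| 4 | 1 | 1 | 0 | 4/20 = 0.20 |
| 4 | 10 | 4 | 0 | 210/4,845 = 0.043 (two-sided 0.087) |
| 4 | 10 | 0 | 1 − 210/4,845 = 0.96 | 1.00 |

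The last row shows the direction problem: two-sided with ties, the same table gives 0.087. Running 10,000 shuffles on two of the tables gave 0.044 against 0.299 (4 responders, 10 carriers, 3 responding) and 0.008 against 0.143 (3, 5, 2), close to the exact values.

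**False-positive rates, if 0.05 were used as a cut-off.** With 4 responders and 10 carriers, the rule as written gives p ≤ 0.05 whenever X ≥ 3, which has probability 29% under no association. The table below averages over binomial numbers of responders and carriers, excluding tables with 0 or 20 of either. Ranges are over assumed carrier prevalences of 10, 25, 50 and 70%.

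| Rule | 20% response rate | 5 to 30% response rate |
|---|---|---|
| As written, one-sided | 22, 17, 19, 30% | 15 to 59% |
| Ties counted, one-sided | 0.3 to 1.4% | 0.01 to 1.6% |
| Ties counted, two-sided | 1.1 to 1.7% | 0.2 to 2.2% |

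An absolute-value version that still excludes ties remains inflated, at 17 to 23% for a 20% response rate. The strict inequality, not the sidedness, is therefore the cause.

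**Continuous marker.** With 4 responders, the strict rule rejected in 5.6% of 2,000 simulations (standard error 0.5%), so there is no material error there.

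**The case against.** The sentence closes an example about expression, where ties hardly matter, and *exceed* may simply be loose wording for at least as large. On that view the plan leaves a tie rule unstated rather than prescribing a wrong analysis. The wording may indeed be loose. But the example is introduced to explain the test for mutation status, it is the only definition given, and an analyst following it would code a strict inequality.

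The analysis is also descriptive, serves a secondary objective and has no alpha, and with 20 patients a reader can look at the underlying table. That stands as a limit on the harm: the false-positive rates measure a decision the plan never formally makes. It does not make an invalid p-value acceptable where the plan has chosen to report one.

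The 59% is a corner case: a 5% response rate with 70% prevalence, driven by tables with very few responders. At a 20% response rate the range is 17 to 30%. All figures are for n = 20. Section 14.1 limits exome and transcriptome sequencing to 10 patients, so predictors found that way would be tested in a smaller sample that these figures do not cover.

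The direction point is weaker, because the mean difference is offered only as an example statistic.

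**Conclusion.** The concern holds: the p-value definition is wrong as written for yes/no mutation status. It always drops the probability of the observed table, and it returns zero when that table is the most extreme in the tested direction. This conclusion does not depend on the illustrative counts; its size does. In the tables worked here with non-zero values, the reported p-value falls from between 0.14 and 0.37 to between 0.009 and 0.043.

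This should be fixed before analysis but is not critical. The response rate, PFS and the sample-size rationale are untouched. The false-positive rates rest on a 0.05 threshold and on carrier prevalences that the documents do not give.

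**What to change.** Replace the sentence in section 14.2 with: two-sided p = (1 + number of shuffles with |T*| ≥ |T observed|)/(10,000 + 1). Alternatively, name Fisher's exact test for yes/no mutation status; with 4 responders there are only 4,845 distinct allocations, so exact enumeration is smaller than the planned 10,000 shuffles. Choose one in advance, because they can differ. With 4 responders and 5 carriers, 2 of them responding, the absolute-difference rule gives 0.53 and Fisher's test gives 0.25. State that these p-values are exploratory.

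The cost is one sentence and no new data. The p-values become larger and the test is conservative: two-sided size is about 1.1 to 1.7% at a 20% response rate and 0.2 to 2.2% over response rates of 5 to 30%. Some margins cannot reach 0.05 whatever the data. The smallest two-sided p-value is 0.087 with 4 responders and 10 carriers, 0.21 with 3 and 10, and 0.20 for a single carrier with 4 responders.

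A mid-p version is less conservative, with average two-sided size of 3.0 to 3.4% at a 20% response rate and about 0.7 to 4.4% over 5 to 30%. It does not guarantee the nominal level: with 4 responders and 10 carriers its size is 8.7%.
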